## **10. RISK/BENEFIT ASSESSMENT**

### **10.1. Potential Risks**

The proposed study is a low risk clinical trial. Subjects (patients & caregivers) will be completing self-report questionnaires at three different regularly scheduled clinic visits. The two topical treatments in the study are FDA-approved and standard care for  $\leq$ moderate atopic dermatitis. Crisaborole is approved for use in ages 2 years and older. Known side effects to crisaborole include pain at the site of application. Tacrolimus 0.03% is approved for use in ages 2 to 15 years. Known side effects to tacrolimus 0.03% include burning sensation, stinging, soreness, or pruritus at the site of application. These localized symptoms may occur during the first few days of use and subside as atopic dermatitis lesions improve. Subjects using tacrolimus should limit sun exposure and should not use ultraviolet light therapy, sun lamps, or tanning beds. Tacrolimus-treated skin should not be covered with bandages, dressings, or wraps. Contact of tacrolimus with eyes or mouth should be avoided. Unexpected side effects, such as allergic reactions, may occur and are unpredictable. This reaction may be mild, such as a skin rash, or you may have more severe symptoms like swelling of the throat, low blood pressure, and shortness of breath. If any of these unexpected side effects occur, subjects will be advised to stop use of their intervention immediately. Subjects will be informed about any additional potential risks if they are discovered. Furthermore, while we make every effort to keep all data and study information private, this cannot be guaranteed. All data will be de-identified and stored in a locked file in a locked office. All appropriate procedures will be taken to maintain subject privacy and data collected during this study.

## **10.2. Protection Against Risks**

Study forms and patient-report forms are either electronic forms through REDCap or paper forms. All data from paper forms will be entered electronically into REDCap database as it is received from the subjects. All electronically captured data will be securely stored in the secure REDCap database at the University of Rochester Medical Center. To protect the confidentiality of subjects, questionnaires and data collected on each subject will be coded, the form collected will contain a numerical Subject ID and Subject Initials. The forms *WILL NOT* contain any personal identifiers. The key list with all Subject IDs will be kept in a locked file. All forms will also be kept in a locked file that is separate from the key list that links the subject name and the code number. When data analyses are completed, the key list and paper forms will be destroyed. The required informed consent will be the only record kept of those subjects who have participated in the research. The interventions that will be studied in this project are not associated with any risks.

Any safety information for an individual patient that is volunteered by a study participant during the course of this research must be reported. All adverse event, whether observed by the Investigator, elicited from, or volunteered by the subject, should be documented. Each adverse event will include a brief description of the experience, the date of onset, the date of resolution, the duration and type of experience, the severity, contributing factors, and any actions taken. This description will be in the summary not during a subject's regularly scheduled clinic appointment.

## **10.3. Potential Benefit to the Subjects**

It is not possible to predict whether subjects will feel any personal benefit from participation in this research study. Subjects may have relief of atopic dermatitis and improved quality of life. The study will provide insight into impact of topical treatments on caregiver burden. Subjects will receive their assigned topical medication free of charge for the duration of

the study. Subjects will receive reimbursement for their participation in this study (See §5.8 on page 18).

#### **10.4. Alternatives to Participation**

Subjects will receive routine standard care with or without participation in this study. Study participation is voluntary. Subjects can be free not to take part or withdraw from the study at any time, for whatever reason.

### **11. DATA ANALYSES AND MONITORING**

#### **11.1. Sample Size Determination**

We will accrue 48 patient and caregiver pairs, accounting for 20% withdrawal or dropout rate, to ensure evaluation of 40 patient and caregiver pairs (i.e., 20 per AD patient/caregiver pairs per topical treatment). All statistical tests will be performed at the two-tailed 0.05 level of significance. For an effect size of 5.0 in a population with standard deviation of 10.0, a sample size of 16 will provide 80% power to detect a score change of 4 in the two primary outcome measures. An electronic medical record search for the last year counted 900 patients with the diagnosis of atopic dermatitis between the ages of 1 and 17 years. However, it is unclear how many of these patients have mild or moderate AD. We will enroll a total of 40 evaluable patients and caregivers (i.e., 20 per AD treatment; 80 total participants). Our sample size will allow us to detect a change of at least 4 (i.e., clinically significant change) in the itch and pain PROs between baseline and 12 weeks of treatment. Subjects that complete at least the 6 week assessment will be considered evaluable. In this study, the superiority of crisaborole is not dependent on the clinical change (EASI); superiority is dependent on significant changes in PROs and their potential correlation with EASI. Therefore, crisaborole would be superior to tacrolimus if crisaborole improves PROs (and/or caregiver burden), but its clinical effectiveness (EASI) is not statistically significantly different than tacrolimus.

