### 1.4 Objectives

**Primary Objective:** To investigate the effect of crisaborole (Eucrisa™) treatment on patient-reported itch and pain in patients with mild to moderate atopic dermatitis compared to tacrolimus 0.03%.

- *Hypothesis:* We hypothesize that crisaborole (Eucrisa™) treatment will significantly decrease (i.e., score change  $\geq 5$ ) the severity of itch and pain over time and these changes will correlate with improvements Eczema Area and Severity Index (EASI) in atopic dermatitis. We further hypothesize that the improvement in these PROs will be greater in the crisaborole treated subjects compared to those receiving tacrolimus.
- *Primary Outcome Measures:* Change in PROMIS® Itch and PROMIS® Pain Interference measures after 12 weeks of treatment.

**Secondary Objective:** To investigate the effect of crisaborole (Eucrisa™) treatment on patient-reported quality of life, sleep, anxiety, and depression in patients with mild to moderate atopic dermatitis compared to tacrolimus 0.03%.

- *Hypothesis:* We hypothesize that crisaborole (Eucrisa™) treatment will improve quality of life and decrease (i.e., score change  $\geq 5$ ) the severity of one or more of the PROs (sleep, anxiety, or depression). These changes will correlate with improvements in atopic dermatitis (EASI). We also hypothesize that the improvement in these PROs will be greater in the crisaborole treated subjects compared to those receiving tacrolimus.
- *Secondary Outcome Measures:* Change in Children’s Dermatology Life Quality Index (CDLQI), PROMIS® Anxiety, PROMIS® Depression, and Children’s Sleep Habits Questionnaire (CSHQ) after 12 weeks of treatment.

**Tertiary Objective:** To elucidate the impact of crisaborole (Eucrisa™) treatment or tacrolimus 0.03% on caregiver burden.

- *Hypothesis:* We hypothesize that improvements in caregiver burden will correlate with improvements in atopic dermatitis (EASI), as well as decreased severity in PROs.
- *Tertiary Outcome Measures:* Change in Caregiver Burden Inventory and Family Dermatology Life Quality Index (FDLQI) after 12 weeks of treatment.

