## 2. STUDY DESIGN

### 2.1. Overview

This is an open-label, randomized, cross-sectional study to monitor the effects of crisaborole and tacrolimus 0.03% on patient-reported outcomes and caregiver burden in children (ages 2 to 15 years, inclusive) with ≤ moderate atopic dermatitis over a 12 week period of time. The goal of this study is to detect changes in PROs and caregiver burden during treatment for atopic dermatitis of moderate or less severity. The study design will allow us to correlate PROs and caregiver burden with treatment response and disease improvement in children.

Additionally, we will be able to determine if crisaborole is a better overall treatment for children with atopic dermatitis compared to tacrolimus 0.03%.

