#### **11.2. Planned Statistical Analyses**

All statistical analyses will be performed at a two-tailed 0.05 level of significance. Descriptive statistics will be performed using the demographic information (i.e., gender, age, race, ethnicity, disease severity) to characterize the patient and caregiver population at baseline. Descriptive statistics will also be utilized to identify PROs most affected by AD and the extent of caregiver burden related to AD. Primary analyses will use ANCOVA, correlative analyses, and regression analyses to identify significant changes in itch or pain interference from baseline to 12 weeks (Baseline Assessment to Treatment Assessment #2). Longitudinal analyses will be performed to examine changes in itch and pain interference over time. Additionally, we will determine the association between itch and pain interference at baseline and over time. Furthermore, we will correlate change in severity of itch and pain interference with change in %BSA of treatable AD. Two-tailed t-tests will compare changes in itch and pain interference between crisaborole and tacrolimus. Secondary and tertiary analyses will employ similar statistical methodology as the primary analyses but to anxiety, depression, sleep, quality of life, and caregiver burden.

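### The 80% power claimed at n = 16 for a 4-point change does not follow from the stated inputs, and the crisaborole–tacrolimus comparison has no stated power

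*Combined protocol and SAP*

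**What the plan says.** Section 11.1 sets a two-sided 0.05 level and 20 evaluable child–caregiver pairs per treatment. Its power sentence opens "For an effect size of 5.0 in a population with standard deviation of 10.0" and concludes that "a sample size of 16 will provide 80% power to detect a score change of 4 in the two primary outcome measures". Later it adds: "Our sample size will allow us to detect a change of at least 4 (i.e., clinically significant change) in the itch and pain PROs", measured between baseline and 12 weeks. It does not name the test, say what the 16 counts (total, per arm or one arm), say whether 10.0 is the SD of scores or of change, or give a correlation.

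Elsewhere the threshold is 5 points. In section 1.4 the hypothesis is that crisaborole "treatment will significantly decrease (i.e., score change" of 5 or more) itch and pain. Section 5.3 takes 5 or more as clinically important for Pain Interference, and gives no threshold or SD for PROMIS Itch.

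The two drugs are to be compared. Section 1.4 hypothesises that "the improvement in these PROs will be greater in the crisaborole treated subjects compared to those receiving tacrolimus". Section 2.1 expects that "we will be able to determine if crisaborole is a better overall treatment for children with atopic dermatitis compared to tacrolimus 0.03"%. Section 11.1 says that "superiority is dependent on significant changes in PROs and their potential correlation with EASI". Section 11.2 plans the test: "Two-tailed t-tests will compare changes in itch and pain interference between crisaborole and tacrolimus". No section gives a target difference, an SD or a power for that comparison.

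**The concern.** The power sentence is the only statistical justification for the sample size. It names two targets, 5.0 and 4, and a reader cannot tell which one, which SD or which contrast the 80% belongs to. It also covers only change from baseline, whereas the superiority claim rests on the difference between drugs. That contrast is harder to detect with 20 per arm. If its power is low and unstated, a null result could be misread as showing that the drugs are equivalent.

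**Working it through.** **Inputs from the documents.** Two-sided 0.05; effect 5.0 and change 4; SD 10.0; n = 16; 20 per arm, 40 in total (section 11.1); 1:1 allocation (section 5.4). The only SDs of change in the documents are in section 1.3: 11 (Pain Interference) and 8.4 (Depression), both from adults starting systemic drugs.

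**Assumption, not in the documents.** Baseline-to-week-12 correlation r of 0.3 to 0.8. For Itch, the SD of 10 and the 5-point target are also assumptions.

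**Step 1: try to reproduce 80% at n = 16, taking SD of change = 10.** For a paired t-test the noncentrality is (Δ/SD)·√n with n − 1 df.
- Δ = 5: 0.5 × 4 = 2.0, power 46% (normal approximation 52%).
- Δ = 4: 0.4 × 4 = 1.6, power 32% (normal approximation 36%).
- 80% power needs n = 34 (5 points) or 52 (4 points). At n = 16 the change detectable with 80% power is 7.5 points.
- One-sided testing gives 60% and 45%. A two-sample test gives 28% and 19% with 16 per arm, and 15% and 11% with 8 per arm.

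None of these is 80%.

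**Step 2: what would make n = 16 work.** 80% power at n = 16 needs Δ/SD = 0.749 (exact t) or 2.8016/4 = 0.700 (normal approximation). With score SD 10, SD of change = 10·√(2(1 − r)), so r = 1 − SD²/200, where SD is the SD of change.
- 5 points: SD of change 6.67 (exact) or 7.14 (normal), so r = 0.78 or 0.75.
- 4 points: SD of change 5.34 or 5.71, so r = 0.86 or 0.84.

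**Step 3: undocumented routes to 16 for 5 points.** With n = (2.8016·SD/Δ)²:
- Route A, score SD 10 and r = 0.75: (2.8016 × 7.071/5)² = 15.7, so 16.
- Route B, SD of change 10: (2.8016 × 10/5)² = 31.4, so 32, which is 16 per arm with arms pooled.

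Each gives 80.7% for 5 points by the normal approximation (exact t 75% and 78%). For the 4 points that the sentence states, the exact t gives 56% and 59%.

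**Step 4: change from baseline at the planned n, SD of change 10.** One arm of 20: 56% (5 points) and 40% (4 points). Both arms pooled, n = 40: 87% and 69%.

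**Step 5: between drugs, 20 per arm.** For the t-test on change, the noncentrality is (Δ/SD of change)·√(20/2) with 38 df. For ANCOVA, the SD is 10·√(1 − r²) with 37 df. At SD of change 10 and Δ = 5: 0.5 × 3.162 = 1.58, power 34%. 80% power is reached only at 9.1 points.

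With score SD 10 (detectable = with 80% power, in points):

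| r | SD of change | Within-arm detectable | t-test power, 5 points | t-test detectable | ANCOVA power, 5 points | ANCOVA detectable |
|---|---|---|---|---|---|---|
| 0.3 | 11.83 | 7.8 | 26% | 10.8 | 37% | 8.7 |
| 0.5 | 10.00 | 6.6 | 34% | 9.1 | 43% | 7.9 |
| 0.7 | 7.75 | 5.1 | 51% | 7.0 | 58% | 6.5 |
| 0.75 | 7.07 | 4.7 | 59% | 6.4 | 64% | 6.0 |
| 0.8 | 6.32 | 4.2 | 68% | 5.7 | 73% | 5.5 |

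80% power for 5 points between drugs is reached at r of about 0.85 (t-test) or 0.84 (ANCOVA). The adult SDs of change, 11 and 8.4, give 29% and 45% with the t-test. These are only indicative.

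**The case against.** The wording about a population with a given SD reads most naturally as the spread of scores. On that reading the plan has left out an input rather than made an arithmetic slip, and the 46%, 32% and 34% hold only if 10 is the SD of change, which equals r = 0.5 at a score SD of 10. This stands: those figures are conditional. It does not rescue the sentence, because the missing input is what would make it true.

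The upper limit of 0.8 on the correlation is also a choice. If the 4-point claim is taken at face value, r is 0.84 to 0.86. Between-drug power for 5 points is then about 77% to 82% (t-test) or 80% to 85% (ANCOVA). Nothing in the documents excludes such a correlation, but nothing supports it, and the plan would have to state and defend it.

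Two further points are fair. Section 11.2 also plans longitudinal analyses, whose precision is not assessed here. Section 2.1 gives detecting change during treatment as the study's goal, and for that the pooled sample is reasonably placed. Neither supplies the missing power for the superiority claim.

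**Conclusion.** The concern holds and must be fixed. The stated 80% cannot be obtained from the stated inputs. It needs either an undocumented correlation of about 0.84 to 0.86 for 4 points, or an undocumented route that works only for 5. The 4-point target conflicts with the 5 points used in sections 1.4 and 5.3. The between-drug comparison has no stated power. For 5 points with 20 per arm, it falls below 80% unless the correlation is at least about 0.84, given a score SD of 10. The size of that shortfall depends on the unstated SD and correlation; the internal conflict and the omission do not.

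**What to change.** Keep the sample size. In section 11.1, replace both the sentence that derives 16 and the later sentence on a detectable change of 4 with one statement, using the sponsor's own SD, correlation and n. For example:

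> The target is 5 points for both primary outcomes. Assuming a score SD of 10 and a correlation of 0.3 to 0.8 between baseline and week 12, 20 children per arm with week-12 data give 80% power (two-sided 0.05) for a within-arm change of 7.8 to 4.2 points (paired t-test), and for a difference between treatments of 10.8 to 5.7 points (t-test on change) or 8.7 to 5.5 points (ANCOVA). Power for a 5-point difference between treatments is below 80% across this range. For PROMIS Itch the SD and the target are assumptions.

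If the sponsor can justify a correlation above 0.8, the figures and the below-80% sentence should be recomputed for it. If the figure 16 is kept, state its test, whether 10 is the SD of scores or of change, the correlation and any pooling of arms, and limit it to a 5-point change from baseline.

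Take n as the number of children expected to give week-12 self-report. Children under 5 complete no itch or pain measure (section 5.1), and subjects seen only to week 6 count as evaluable (section 11.1), so n can fall below 20 per arm. With 16 per arm, for illustration, the between-drug detectable difference (t-test on change) is 12.1 to 6.5 points over the same correlations.

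The cost is wording in section 11.1, with no added patients, visits or tests. The stated power becomes less favourable, and the sponsor must commit to an SD and a correlation.

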### 3.5. Inclusion Criteria:

#### Pediatric Subjects:

- a) Male and female subjects of inclusive ages of 2 to 15 years at screening visit.

- b) Diagnosis of  $\leq$ moderate atopic dermatitis or eczema (ISGA 2 or 3 and  $\geq 3\%$  BSA, excluding scalp).
- c) If subject is taking or prescribed antihistamines, subject must be on stable dose of antihistamines.
- d) If subject is taking topical steroids, subject must be on stable dose of topical steroid.
- e) Subjects currently taking tacrolimus (i.e., Protopic), crisaborole (i.e., Eucrisa), or other topical steroid-sparring medications are eligible for this study if he/she agrees to a two week “washout period” prior to starting study procedures (See “washout period” described below on page 9).
- f) If subject is taking systemic anti-inflammatory therapy (i.e., cyclosporine, etc), subject must be on a stable dose of the systemic anti-inflammatory medication for at least six week prior to enrollment and it must be anticipated that this dose would not change during their participation in this study, unless deemed medically necessary. Any changes in medication dose due to flaring of atopic dermatitis or side effects will be documented on the *AD Flare Medication Form* and *AE Source Doc* (see page 19).
- g) Caregiver (i.e., adult parent or guardian) must agree to participate in the study with the patient.
- h) Subject must be able to read and speak English.
- i) Subject, ages  $\geq 8$  years, is able to give assent.

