**4.2. Informed Consent Process**

Study personnel and/or dermatologist will identify eligible subjects. Eligible subjects will first be asked if they wish to hear about a potential clinical trial for atopic dermatitis. If the subject expresses interest in the study, the study personnel will approach the subject to discuss the study and obtain informed consent/assent from the patient and caregiver.

All study materials are in English, therefore all subjects must be able to read, speak, and understand English. Current FDA, ICH, NCI, state, federal, and institutional regulations concerning informed consent will be followed. Verbal assent will be obtained from pediatric subjects using the study Verbal Assent Script. Study personnel will read the verbal assent script to the pediatric subject and parent, answer all questions, and complete the form if the subject wishes to participate. All pediatric subjects (ages 8 to 12 years) must provide assent using Assent Form 1 and have their parent (i.e., adult caregiver) provide consent for participation in this study. All pediatric subjects (ages 13 to 15 years) must provide assent using Assent Form 2 and have their parent (i.e., adult caregiver) provide consent for participation in this study. Assent is not required for pediatric subjects less than 8 years old; however parent consent and permissions is required. Study personnel will discuss the informed consent form with the adult caregiver subjects (i.e., parent or guardian). The informed consent for will be a dual consent form on which the adult subject consents to participation as a caregiver in the study and also consents to their child's participation in the study. Additionally, during the consent process both subjects will be asked to complete a W9 form for reimbursement purposes. The adult subject will provide their name, mailing address, and signature on the Study Reimbursement Form to ensure that reimbursement can be mailed to him/her after study participation has completed.

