  - *Pediatric Subjects:* Pediatric subjects ( $\geq 5$  years) will complete five self-report outcome measures (**PROMIS® Itch, PROMIS® Pain Interference, Children's Dermatology Life Quality Index (CDLQI), PROMIS® Anxiety, PROMIS® Depression**) on an iPad. All self-report measures can be completed with the assistance of their parent or guardian. All five self-report outcome measures can be completed in 20 minutes or less. Pediatric subjects  $< 5$  years will not complete any self-report measures on the iPad.
  - *Caregiver Subjects:* All caregivers will complete one self-report questionnaire about their child's sleep habits (**Children's Sleep Habits Questionnaire (CSHQ)**) and two self-report measures for caregiver burden (**Caregiver Burden Inventory (CBI)**) and quality of life (**Family Dermatology Life Quality Index (FDLQI)**) on an iPad. All self-report measures can be completed in 5 minutes.
- Pediatric subjects will complete a Pediatric Subject Reimbursement Form at the end of the Baseline Assessment. The pediatric subject will print their name, address, sign and date the form. The adult caregiver may help the child complete the form if he/she has difficulty writing. Pediatric subject  $\geq 5$  years must sign the form. Study personnel will give the pediatric subject a \$10 gift card after for the completion of this form for completion of the Baseline Assessment. For pediatric subjects  $< 5$  years, the adult caregiver will complete and sign the form. Study personnel will give the adult caregiver subject a \$10 gift card after for the completion of this form for completion of the Baseline Assessment.
- Study personnel will call the caregiver by phone during the Week 3 of treatment for adverse event monitoring of their child who is participating and on topical treatment. Study personnel will ask: 1) Has your child been able to use the topical treatment without any problems?; 2) Has your child experienced any burning from the topical treatment?; and 3) Has your child experienced any side effects or adverse reactions while using the topical treatment?. Study personnel will document the phone call in the Call Log. Adverse events will be documented on AE source doc.
- Study personnel will call the caregiver by phone at least 48 hours prior to the 6 Week Assessment to remind he/she of their upcoming appointment and to bring their tube of topical treatment with them to the appointment. Study personnel will also monitor for

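### Section 11.1 counts children as evaluable who have no itch or pain score, so 40 evaluable pairs need not give 20 per arm for the primary analysis

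*Combined protocol and SAP*

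**What the plan says.** Section 11.1 sets the target: "We will enroll a total of 40 evaluable patients and caregivers (i.e., 20 per AD treatment; 80 total participants"). It says this sample will detect a change of at least 4 points "in the itch and pain PROs between baseline and 12 weeks of treatment". Its only definition of evaluable is: "Subjects that complete at least the 6 week assessment will be considered evaluable". The primary outcomes in section 1.4 are "Change in PROMIS® Itch and PROMIS® Pain Interference measures after 12 weeks of treatment", and section 11.2 runs the primary analyses from baseline to 12 weeks.

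Section 3.5 admits children aged 2 to 15. For the baseline, 6-week and 12-week visits alike, section 5.1 says that subjects under 5 "years will not complete any self-report measures on the iPad". Caregivers complete the CSHQ, CBI and FDLQI, none of which is an itch or pain score.

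Two statements bear on how many under-5s will enrol, and they point in different directions. Criterion (h) for pediatric subjects reads "Subject must be able to read and speak English", and section 4.2 adds: "All study materials are in English, therefore all subjects must be able to read, speak, and understand English". Yet section 5.1 also sets out reimbursement steps at each visit for children under 5 "years, the adult caregiver will complete and sign the form".

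**The concern.** The figure of 20 per arm is offered as the basis for the 12-week itch and pain result. The set that is counted to reach it differs from the set that can supply that result, in two ways.

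The main one is age. A 3-year-old who attends every visit is evaluable under section 11.1 and has no value for either primary outcome. The trial could therefore report its target as met with fewer than 20 children per arm behind the primary comparison, and the plan would not show it.

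The second is timing. A child aged 5 or over who has week 6 but not week 12 is also evaluable, without the 12-week change that defines the primary outcome.

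The consequences differ. The age gap costs precision and does not itself bias the comparison, because age is fixed before randomisation. Loss between weeks 6 and 12 comes after randomisation, may depend on outcome, and could bias it.

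**Working it through.** **The plan's own sample-size figure.** Section 11.1 says a sample of 16 gives 80% power for a change of 4, citing an effect of 5.0, an SD of 10.0 and a two-sided 0.05 level. It does not say whether 16 is per arm or in total. By noncentral t with SD 10, 16 per arm in a two-sample test has 28% power for 5 points and 19% for 4; a one-sample test of change with n = 16 has 46% and 32%. The figure does not reproduce. That is a separate problem, and nothing below depends on it.

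**Inputs.** From the documents: 40 evaluable pairs at 1:1 (sections 11.1 and 5.4), up to 48 accrued with a 20% dropout allowance (sections 3.1 and 11.1), two-sided 0.05, and two-tailed t-tests between arms (section 11.2). Assumed: an SD of 10 for the change score (section 11.1 gives 10.0 without saying whether it is for a score or a change), and the under-5 share f.

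Range for f: 0% if criterion (h) is applied literally; 10%; 21% if ages are spread evenly (3 of the 14 single-year ages from 2 to 15, 3/14 = 21.4%); and 40% as an upper case with no basis in the documents.

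**Scored children among 40 evaluable pairs.** Number = 40 × (1 − f); per arm, n = 20 × (1 − f). The detectable difference is the value at which the two-sample noncentral t-test reaches 80% power, with noncentrality difference / (10 × √(2/n)) and 2n − 2 degrees of freedom. No loss after week 6 is applied.

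| f | Scored children | Per arm | Detectable difference | Power for 5 points |
|---|---|---|---|---|
| 0% | 40 | 20 | 9.1 | 34% |
| 10% | 36 | 18 | 9.6 | 31% |
| 21% | 31.4 | 15.7 | 10.3 | 27% |
| 40% | 24 | 12 | 12.0 | 22% |

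**Do existing provisions close the age gap?** The 20% allowance is for withdrawal or dropout, and section 7 replaces subjects who withdraw. An under-5 who completes is neither. Section 5.4 describes no age stratification, and no section caps under-5 enrolment.

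**Loss after week 6.** Section 7 replaces withdrawals with no cut-off at week 6, and lists loss to follow-up and inability to attend visits among its withdrawal criteria. Read literally, a child withdrawn between weeks 6 and 12 is replaced. Whether numbers are restored then depends on whether the replacement fits within the ceiling of 48 in section 3.1.

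**What 48 pairs deliver.** With 20% loss and no replacement, the number with week 12 is 48 × (1 − f) × 0.8. Even at f = 0 this is 38.4 rather than 40, because 48 is 40 × 1.2, whereas 40/0.8 = 50.

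| f | Aged 5 or over, of 48 | With week 12 | Per arm | Detectable difference (unadjusted) |
|---|---|---|---|---|
| 0% | 48 | 38.4 | 19.2 | 9.3 |
| 10% | 43.2 | 34.6 | 17.3 | 9.8 |
| 21% | 37.7 | 30.2 | 15.1 | 10.6 |
| 40% | 28.8 | 23.0 | 11.5 | 12.2 |

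The two tables use different attrition: the first starts from 40 evaluable pairs, the second from 48 accrued.

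**The case against.** **The shortfall may be small or nil.** Criterion (h) and section 4.2, taken literally, would exclude most children under 5. At 10% the detectable difference moves only from 9.1 to 9.6 points. This stands as a limit on size. It does not remove the gap, because section 5.1 provides for under-5s at every visit. A reader might infer that the trial will fall short of 20 per arm. The documents do not support that: with no under-5s and no loss after week 6 there is no shortfall.

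**Losses after week 6 may be made good.** A reader might also infer that every such child is lost to the primary analysis for good; a 10% loss would then cut 40, 36, 31 and 24 to about 36, 32, 28 and 22. That assumes no replacement, which section 7 does not say. What remains is the ceiling of 48 and the fact that a replacement restores numbers without removing bias from outcome-related loss. On bias, section 6 withdraws children newly given systemic therapy for worsening disease, but says such therapy is unusual at this severity. Section 8 keeps flaring children on study, and section 5.1 allows a telemedicine week-12 visit. The route is possible; nothing suggests it is common.

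**Longitudinal analyses are already planned.** Section 11.2 includes them, and they could use week-6 scores from children aged 5 or over. They cannot supply a score for an under-5, and section 11.2 does not say which of its methods gives the between-arm result.

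**This is a minor part of the power problem.** That stands. At 20 per arm, power for 5 points is already 34%.

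**Conclusion.** The point holds as one of definition and reporting. Evaluable in section 11.1 does not mean able to contribute to the primary analysis, and every under-5 enrolled widens the difference. The statement that 40 evaluable pairs need not give 20 per arm follows from the text and needs no assumption about age mix. Its size does: the detectable difference rises from 9.1 points with no under-5s to 10.3 at a 21% share and 12.0 at 40%, all at an assumed change SD of 10. Criterion (h) favours the low end.

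The week-12 part is secondary. Its effect on numbers turns on how section 7 is applied within 48 pairs, and its potential for bias is real but of unknown size. The point should be corrected because the change is cheap and the stated size is one the design need not deliver.

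**What to change.** 1. **Section 11.1, analysis sets.** Keep the all-age evaluable set for EASI, CSHQ, CBI and FDLQI. Define the primary patient-reported set as randomised children aged 5 or over with baseline itch and pain scores.
2. **Section 11.1, numbers.** State the expected size of that set, the expected number with a week-12 score, and the detectable difference over a stated range of under-5 shares. The second table above is a starting point: about 38, 35, 30 and 23 children with week 12, and 9.3, 9.8, 10.6 and 12.2 points. Replace the assumed share with the observed one when it is known.
3. **Section 11.2 and section 7.** Name a baseline-adjusted longitudinal model using weeks 6 and 12 as the source of the between-arm result, so that children with week 6 only contribute. The precision gain is small. At a 21% share, with all correlations 0.5 and all 20% loss after week 6, the effective number per arm is 1/[(8/9)/15.09 + (1/9)/18.86] = 15.4, against 15.1. The main value is that week-6 scores inform the estimate when week 12 is missing. State whether a child lost after week 6 is replaced, and whether replacements count within the 48.
4. **Sections 3.5, 4.2 and 5.1.** Reconcile the English-reading requirement with the under-5 procedures.

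The cost is wording and one named model, with no added subjects or visits. The downside is that the stated primary n and detectable difference become less favourable. These changes correct the stated figures; they do not restore 20 per arm.
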